11.3. The Level of Statistical Significance

$P < 0.05$ will be used to demonstrate statistical significance.

11.4. Criteria for the Termination of the Trial

We would only anticipate 10 episodes of severe hypoglycaemia in 340 patients per year. Therefore the likelihood of a severe hypo occurring during this study under normal circumstances would be very small. So if we assume there is no increase in risk then we would only expect to see 2 severe hypos in one of the two arms in 3 out of every 10,000 trials, for a single hypo in either arm this increases to about 1 in every 100 trials. Therefore we would terminate the trial if we had 2 severe hypos occurring on any arm of the trial.

11.5. Procedure for Accounting for Missing, Unused, and Spurious Data.

We will use boxplots to identify outlying, unusual or spurious data using pre-defined decision rules (e.g. upper or lower quartiles $\pm 1.5 \times \text{IQR}$). In the case of implausible or unlikely outcome data we will look back at CRF's to rule out data handling errors. If outliers cannot be resolved then we will exclude this particular result from the main analysis. We intend to use a complete case analysis but we will conduct a sensitivity analysis to assess the impact of any missing data using appropriate multiple imputation methods.

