8.7. Discontinuation/Withdrawal of Participants from Trial Treatment

Each participant has the right to withdraw from the trial at any time. In addition, the Investigator may discontinue a participant from the trial at any time if the Investigator considers it necessary for any reason including:

- Pregnancy
- Ineligibility (having been overlooked at screening)
- Significant protocol deviation
- Significant non-compliance with treatment regimen or trial requirements
- Severe hypoglycaemia occurring during the trial week, whether or not this is as a result of the evening meal dose of insulin
- Withdrawal of Consent
- Loss to follow up

Any CGM data available up to the time of patient withdrawal or exclusion will be included in the data analysis.

The reason for withdrawal will be recorded in the CRF.

If the participant is withdrawn due to an adverse event, the Investigator will arrange for follow-up visits or telephone calls until the adverse event has resolved or stabilised.

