11.2. The Number of Participants

We estimate that using a three-treatment, three period cross-over design, 36 people will achieve 80% power to detect a 2 mmol/L difference in mean 5 hour postprandial glucose excursion at the 5% significance level. Although we do not anticipate any losses to follow-up or withdrawals due to side-effects from the study we will aim to recruit 40 to ensure power is maintained if this does arise. This power calculation has been carried out by our study statistician.

In order to allow for drop-outs, we have made the decision to recruit 40 patients.

Previous intervention studies of fat/protein interventions in children using insulin pumps have used 24-42 patients with significant differences in BG levels at the 0.04 and 0.03 levels of significance (5-8).

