11.6. Inclusion in Analysis

All data available from all participants will be used for the analyses. If a child has become hypoglycaemic (BG $< 4.0 \text{ mmol/l}$) during the profile period then subsequent data will be analysed separately. If any child has had to treat a high BG level with additional insulin (except for a correction dose at the evening meal), then subsequent profile data will be analysed separately. However in either instance, the data up to the event will be included in all analyses. The two other meals would still be eligible for the study analyses if there were no similar events.

If there have been any protocol breaches, such as further food during the evening after the main meal, then all the subsequent data will not be used in the analysis for that meal. Education of the participants and parents will be vital to ensure that such eventualities are rare.

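### Section 11.5 makes an undefined complete-case analysis the main one while Sections 11.6 and 8.7 keep partial data, and the step from 36 to 40 children makes no allowance for lost meals

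*Combined protocol and SAP*

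**What the plan says.** Section 11.5 states the main approach: "We intend to use a complete case analysis". The same sentence adds a sensitivity analysis by multiple imputation as the back-up. It does not define a case.

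Section 11.6 opens with a different rule: "All data available from all participants will be used for the analyses". When a child becomes hypoglycaemic or takes extra corrective insulin, later data from that profile are set aside, but "the data up to the event will be included in all analyses". For the rest of that child's evenings, "The two other meals would still be eligible for the study analyses if there were no similar events".

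Section 8.7 adds, for children who leave: "Any CGM data available up to the time of patient withdrawal or exclusion will be included in the data analysis".

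Section 11.2 gives the sample size: "36 people will achieve 80% power to detect a 2 mmol/L difference" in the 5-hour mean excursion at the 5% level. It then says "we will aim to recruit 40 to ensure power is maintained". The reasons given are loss to follow-up, withdrawal and drop-out. Lost meals are not mentioned.

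Section 11.1 plans paired t tests, or Mann-Whitney U tests for non-normal data. It gives no rule for a child with two usable meals.

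**The concern.** Each child contributes three meals, so the definition of a case decides who is analysed. If it means a child with all three meals, one spoilt evening removes two good ones, which Section 11.6 says stay in. If it means a single complete meal, a profile stopped by an event is incomplete, yet Section 11.6 keeps its early part in every analysis. Section 8.3 says the study is unblinded, so leaving the choice open allows the analysis set to be settled after the results can be seen.

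The plan itself creates several routes to losing a meal or part of one:

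- hypoglycaemia or corrective insulin (Section 11.6);
- a breach such as later food (Section 11.6);
- a dose not given, or mistimed by more than 15 minutes (Section 9.3);
- an unresolved outlier (Section 11.5).

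The primary measure covers 8 hours after an evening meal, so the exposure runs overnight. Two things are at stake: power, because the recruitment margin is counted in children only; and selection, because hypoglycaemia and correction are themselves glucose outcomes.

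**Working it through.** **1. The three rules applied to the same child.** Take a child with two clean evenings and one profile stopped by hypoglycaemia at hour 4.

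| Rule | Clean meals | Stopped meal |
|---|---|---|
| 11.5, case = child with three complete meals | dropped | dropped |
| 11.5, case = pair | the one clean pair is kept | dropped |
| 11.5, case = meal | kept | dropped |
| 11.6 | kept | kept to hour 4 |

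No reading of Section 11.5 reproduces Section 11.6 for this child. For the 8-hour primary measure the difference disappears only if the event comes after hour 8.

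**2. The plan's own figure.** Inputs from Section 11.2: n = 36, power 80%, difference 2 mmol/L, alpha 5% (two-sided assumed). No SD or correlation is given, so the 36 cannot be reproduced; it can only be solved backwards.

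- Normal approximation: SD of paired differences = 2 × √36 / (1.960 + 0.842) = 12 / 2.802 = 4.28 mmol/L.
- Paired t test (noncentral t): SD = 4.16 mmol/L, so within-child SD = 4.16 / √2 = 2.94.

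The 4.16 is used below. It is an assumption, not a figure from the documents, and it belongs to the 5-hour measure.

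**3. The margin.** 36 / (1 − 0.10) = 40, so 40 covers exactly a 10% loss of children. Forty children give 40 × 3 = 120 meals.

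**4. Proportion of meals lost, p, that uses up the margin.**

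- All three meals required, independent losses: 40(1 − p)³ = 36, so p = 1 − 0.9^(1/3) = 3.45%, or 4.1 of 120 meals.
- Both meals of a pair required (the paired t test), independent losses: 40(1 − p)² = 36, so p = 1 − 0.9^(1/2) = 5.13%.
- Losses fully clustered in four children: 12 / 120 = 10%.

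Under the three-meal rule, the chance of at least 36 complete children is 63% at 3.45% loss, 31% at 5% and below 1% at 10%.

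**5. Power at illustrative loss rates.** The documents give no rate. Meals are lost at random, the SD is 4.16 and the difference is 2 mmol/L.

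| Meals lost | Three-meal complete case | Paired t test, available pairs | Within-child model, all remaining meals |
|---|---|---|---|
| 10% | 40 × 0.9³ = 29.2 children, 70–71% | 40 × 0.9² = 32.4 pairs, 75–76% | 77–80% |
| 20% | 40 × 0.8³ = 20.5 children, about 54% | 40 × 0.8² = 25.6 pairs, about 65% | about 70% |

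The first two columns come from the noncentral t distribution and agree with simulation. The last comes from simulation, with the spread at 10% reflecting separate runs and small modelling differences.

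**The case against.** The strongest reply is that Section 11.5 never says a child must have all three meals. The outlier rule just before it removes a single result, not a child, and Section 11.6 keeps the other meals. Read as complete meals or pairs, Section 11.5 comes close to Section 11.6. The planned paired t test needs only two meals. This stands. A reader might infer that complete case certainly discards good meals, that the margin is gone at 3.5%, and that a mixed model gains 6 to 10 points of power at 10% loss and 16 at 20%. The documents do not support those as facts, because they are the consequences of one reading. Against available pairs, the gain is roughly 1 to 5 points at 10% and 5 at 20%.

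The plan also limits the damage. Multiple imputation is already promised, evenings abandoned before the meal are repeated (Section 6.3), and a failed sensor is re-sited (Section 10.3). Section 11.6 aims to keep breaches rare through education. No rate of meal loss is given, so calling heavy loss likely would go beyond the text.

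A reader might also infer that a mixed model removes the selection problem. It does not. Profiles are cut short because of that same meal's glucose, so missing at random is doubtful for them, and the random-loss calculation says nothing about this bias.

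The reply does not supply a definition of a case, reconcile Section 11.5 with the early part of a stopped profile, or provide an allowance for lost meals.

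**Conclusion.** The concern holds as an inconsistency in the analysis set together with an unstated allowance. Sections 8.7, 11.5 and 11.6 cannot all be followed as written. If meals are lost, the margin of four children is exhausted somewhere between about 3.5% and 10% of meals, depending on what counts as a case and how far losses cluster; 5.1% is the figure for the planned paired t test with independent losses. The power cost relative to a within-child model is modest if pairs are used and large only if all three meals are required. All power figures rest on the back-solved SD, two-sided 5% testing, random loss and assumed loss rates. They concern the 5-hour measure in Section 11.2, not the 8-hour primary outcome. The point should be corrected before analysis, but it does not show that the trial is underpowered.

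**What to change.** - Make the main analysis one within-child mixed model on all available meals, with child as a random effect and insulin timing and period as fixed effects.
- Align Sections 8.7, 11.5 and 11.6 to that rule, and say how a profile that stops before 8 hours enters the primary measure.
- Define a case, and keep complete case as a sensitivity analysis beside the planned multiple imputation. At least one sensitivity analysis should address profiles cut short by the meal's own low or treated high glucose, where missing at random is doubtful.
- In Section 11.2, state the SD used and an allowance for lost meals, given as a range with its assumptions.

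The cost is revised wording and a standard model; no extra children, visits or data are needed. The downside is the model's reliance on missing at random, which is why the sensitivity analyses have to stay.

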6. TRIAL DESIGN

6.1. Summary –

The study design is a repeated measures study involving the provision of a standard high protein/high fat evening test meal on 3 different evenings within a 7-day period in the same study subject. The children/adolescents will be instructed to give an insulin dose for the carbohydrate before the meal (calculated using their optimal insulin to carbohydrate ratio (ICR)). In addition they will have an extra dose for the fat and protein content either before (together with the dose for the carbohydrate in the meal [control meal]), 1 hour after, or 2 hours after the first insulin dose given before the meal. These will be carried out in a random order in each subject. Glucose monitoring will be carried out using CGM for the whole 7 day period.

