Participants will be asked not to give a correction dose before the meal if the BG level is between 7-12mmol/l as this would interfere with the analysis. They will be asked, if possible, not to carry out the test meals if their pre-meal BG is greater than 12 mmol/l. But if they have to do the test meal with a high pre-meal BG (above 12 mmol/l) they will be instructed to give their usual correction bolus in addition to the prescribed insulin dose for the test meal. This data will be analysed separately. If BG is below 4mmol/l (hypoglycaemic) or above 16mmol/l participants will be asked to abandon the study evening and repeat on another evening. Full written instructions will be provided to the family for all aspects of the insulin dosing for the study meals.

During the study on the standardised meal days children will be instructed not to eat any food after the meal during the evening, and not to correct any later BG levels unless they are dangerously high (BG over 16 mmol/l with ketones over 0.5 mmol/l). If BG levels go low at any time (BG less than 4 mmol/l) children will be instructed to treat the hypoglycaemia according to their usual management, and omit

any further study doses of insulin if the hypoglycaemia occurs after a first study dose and a second is due. This data will be analysed separately. Children and families will be asked to complete diaries during the trial week.

At the end of the study period (the day after the third meal), children will come back to the research facility or clinic for the end of study visit (visit 3). A research nurse or dietitian will remove the CGM sensor and download the data onto a secure laptop. Children and their families will then be asked to complete a short questionnaire about the acceptability of using the extra insulin doses, and their perceptions as to whether there were any beneficial or adverse effects.

The study dietitian will calculate standard outcomes from each patient's sensor download and pass on anonymously to the study statistician to analyse the data.

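### The planned multiple imputation does not test the rules that set aside recorded CGM readings after a low, a treated high or further food

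*Combined protocol and SAP*

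**What the plan says.** Section 11.5 sets the main analysis: "We intend to use a complete case analysis". It then names one sensitivity analysis: "we will conduct a sensitivity analysis to assess the impact of any missing data using appropriate multiple imputation methods". It does not say what counts as missing, or which variables or model the imputation would use.

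Section 11.6 opens by promising to use all available data, then sets some aside. If BG falls below 4.0 mmol/l "during the profile period then subsequent data will be analysed separately". If a high is treated with additional insulin, other than a correction at the evening meal, "then subsequent profile data will be analysed separately". In both cases the readings before the event stay in every analysis. After a protocol breach such as further food, "then all the subsequent data will not be used in the analysis for that meal".

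The set-aside readings normally exist. Section 6.1 states: "Glucose monitoring will be carried out using CGM for the whole 7 day period". Section 6.3 adds that the sensor records every 5 minutes.

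Two instructions in section 6.3 bear on the triggers. Children are told "not to correct any later BG levels unless they are dangerously high", meaning BG over 16 mmol/l with ketones over 0.5 mmol/l. After a low, any second study dose still due is omitted.

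The primary outcome in section 5 is the mean excursion over 8 hours. No section says what the separate analysis consists of, plans a count of set-aside evenings by timing, or compares the timings with every recorded reading kept.

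**The concern.** The randomised factor is when the extra insulin is given, and the outcome is glucose. A low or a treated high is a consequence of both, so the rules can remove different shares of the 8-hour profile at different timings. An early low removes most of the profile. Section 6.3 adds an asymmetry: only the 1-hour and 2-hour evenings have a second dose that a low can cancel.

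A reader of the eventual report would look to the sensitivity analysis to see whether these exclusions matter. If it leaves the same recorded readings out, agreement with the main analysis says nothing about them. What is at stake is how far the reported ranking of the three timings depends on the set-aside rules.

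**Working it through.** **The plan's own figures.** The documents give no event rate and no expected share of readings set aside. The nearest figure is section 11.2: 36 participants for 80% power to detect 2 mmol/l in the 5-hour excursion. No SD is stated, so 36 cannot be reproduced. It is not in dispute here, and the 2 mmol/l serves only as a yardstick.

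**Step 1: two readings of section 11.5.**
- Set-aside readings are not missing. Imputation then fills only what the sensor failed to record, and the set-aside readings stay out.
- Set-aside readings are missing. They are then blanked and replaced by predictions from pre-event readings and other meals.

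Either way, changing the set-aside values changes neither the complete-case nor the imputed result. The exception would be an imputation model that used those readings as predictors, which nothing in 11.5 suggests.

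**Step 2: how far the recorded result can move.** Let f be the share of the 8-hour readings set aside at a timing, and Δ a change in the level of those readings. The recorded mean at that timing moves by f × Δ. The difference (2 h minus before) moves by (f at 2 h − f before) × Δ. The imputed difference moves by 0.

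This was checked in a simulation of 60,000 children with 5-minute profiles over 8 hours, each cut at the first reading below 4.0 mmol/l. Event rates, curve shapes, SDs and the rise after a treated low (2, 3 or 5 mmol/l) are all assumptions. Going from a rise of 2 to a rise of 5 gives Δ = 3.
- Scenario A (a low on 37% of before evenings and 15% of 2-hour evenings; f = 0.332 and 0.091): (0.091 − 0.332) × 3 = −0.72. Simulated: −0.48 − 0.22 = −0.70.
- Scenario B (12% and 28%; f = 0.104 and 0.138): (0.138 − 0.104) × 3 = +0.10. Simulated: −1.18 − (−1.27) = +0.09.
- Equal case (16% each, identical curves; f = 0.122 each): 0. Simulated: about 0.

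**Step 3: methods side by side.** Difference in 8-hour mean excursion, 2 h minus before, mmol/l:

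| Method | A, rise 2 / 3 / 5 | B, rise 2 / 3 / 5 | Equal |
|---|---|---|---|
| All recorded readings | +0.22 / −0.01 / −0.48 | −1.27 / −1.24 / −1.18 | about 0 |
| Mean up to the event | +1.05 | −0.92 | about 0 |
| Complete case, paired | +0.50 | −1.07 | about 0 |
| Imputation, missing at random | −0.01 | −1.37 | about 0 |

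The last three rows do not vary with the rise. Gaps from the all-recorded row run from 0.00 to 1.05 − (−0.48) = 1.53 in A, and from 0.10 to −0.92 − (−1.27) = 0.35 in B. In A with a rise of 5, complete case and all-recorded have opposite signs. The equal case has no timing effect to distort, so it does not show that equal event rates alone are harmless.

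Rows two and three also differ from each other (+1.05 against +0.50 in A). Section 11.6 points to the former and 11.5 to the latter.

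**Step 4: the separate analysis.** It holds only post-event segments of meals that had an event. If it were run as a paired comparison, which the plan does not say, the expected number of children with a low on both of two given evenings is 40 × [p² + ρp(1 − p)]. With p = 0.20 assumed:
- ρ = 0: 40 × 0.04 = 1.6
- ρ = 0.4: 40 × (0.04 + 0.064) = 4.2

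Over the same two values of ρ, the range is 0.4 to 1.8 at p = 0.10 and 3.6 to 7.0 at p = 0.30.

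**The case against.** The strongest reply is that sections 11.5 and 11.6 cover different things: imputation for data never recorded, a separate route for data recorded after an event. That is a fair reading, and a reader who infers that 11.5 will overwrite known values goes beyond the text. On this reading, however, the set-aside rules have no sensitivity analysis at all.

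A second reply concerns missing at random. A reader might infer that it must fail because glucose triggers the loss. But the low that cuts the profile is itself observed, and pre-event readings are kept. A model that conditions on that history can be consistent with missing at random, and its gap from complete case would reveal some selection. That stands. Such a model estimates the course without the event, which is still not a comparison with the rules switched off.

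Third, the all-recorded result is not the truth against which the others are biased. It mixes timing with rescue treatment and with second doses omitted on the 1-hour and 2-hour evenings. Asking about timing without these is legitimate. This stands, and it is why the added analysis should supplement the main one.

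Fourth, section 5 already collects all lows, and BG above 12 mmol/l, as a safety outcome. That shows how often lows occur, but not their effect on the primary comparison.

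**Conclusion.** The point holds as a cheap improvement. Readings that the sensor normally records leave the timing comparison on post-randomisation triggers that can depend on timing, and no planned analysis puts them back. The absence of a check follows from the text of 11.5 and 11.6 and needs no simulation.

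The size and direction of the effect are unknown. Under assumed traces the shift ran from about 0 to 1.5 mmol/l, the top being about three-quarters of the 2 mmol/l yardstick, which itself refers to 5 hours. Only lows were simulated, and part of any shift is a change of question and not an error.

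A reader might also infer that most lost readings go because glucose ran low or high. The documents do not support this. They give no rates, and the trigger for treating a later high is narrow. Data can also be lost through further food, wrong dose or timing (section 9.3), unresolved boxplot outliers (11.5) or sensor failure (10.3).

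**What to change.** - In 11.5, add a sensitivity analysis that repeats the primary timing comparison on all recorded readings to 8 hours for every randomised test meal, regardless of a low, a treated high or further food. Report it beside the main analysis.
- In 11.5, restrict multiple imputation to readings the sensor did not record.
- In 11.6, define the separate analysis as descriptive: the number of set-aside evenings and their data, by timing.
- Reconcile the complete-case statement in 11.5 with the retention of pre-event readings in 11.6, and say how an 8-hour mean is formed from a cut profile.
- Reconcile 6.3 with 11.6 on meals begun above 12 mmol/l with a correction dose. The former analyses them separately; the latter exempts an evening-meal correction.

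The cost is some wording and one more run on data already downloaded. No clinical instruction changes. The downside is that the recorded traces carry the effects of rescue treatment and omitted second doses, so the added analysis cannot replace the main one.
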